## 6.2 Exclusion criteria

Study participants are not permitted to enroll in the study if any of the following criteria is met:

1. Study participant has previously received IMP in this study.
2. Study participant has participated in another study of an IMP (or a medical device) within the previous 3 months before Screening (or within 5 half-lives for the IMP, whichever is longer) or is currently participating in another study of an IMP (or a medical device).
3. Study participant has a history of drug or alcohol dependency within the previous 6 months or tests positive for alcohol (breath test) and/or drugs of abuse (urine test) at the Screening Visit.
4. Study participant has a current or past psychiatric condition that, in the opinion of the Investigator, could compromise his/her safety or ability to participate in this study or a history of schizophrenia, or other psychotic disorder, bipolar disorder, or severe unipolar depression. The presence of potential psychiatric exclusion criteria will be determined based on the psychiatric history collected at Screening.
5. Study participant has a lifetime history of suicide attempt (including an [REDACTED]), or [REDACTED] as indicated by a positive response (“Yes”) to either Question 4 or Question 5 of the “Screening/Baseline” version of the C-SSRS at Screening.
6. Study participant has any medical condition that, in the opinion of the Investigator, could jeopardize or would compromise the study participant’s ability to participate in this study.
7. Study participant has a known hypersensitivity to any components of the IMP as stated in this protocol.
8. Study participant has made a blood or plasma donation or has had a comparable blood loss (>400mL) within the last 3 months prior to the Screening Visit.
9. Study participant has a consumption of more than 3 units of alcohol/day in case of females, more than 4 units of alcohol/day in case of males.
10. Study participant smokes more than 5 cigarettes per day (or equivalent) or has done so within 6 months prior to the Screening Visit.
11. Study participant has a consumption of more than 600mg of caffeine/day (200mL of coffee contains approximately 100mg of caffeine, 200mL of black tea approximately 30mg, and 200mL of cola approximately 20mg).
12. Study participant has a diet, which deviates notably from the “normal” amounts of protein, carbohydrate, and fat, as judged by the investigator (eg, vegetarians or vegans).
13. Study participant is taking any concomitant medication currently or within 2 weeks prior to the first day of dosing with the exception of paracetamol (acetaminophen) which is allowed to be taken orally up to 1000mg per dose (up to 2000mg per day).
14. Study participant has received any prescription or nonprescription medicines, including enzyme inhibitors or inducers, over-the-counter (OTC) remedies, herbal and dietary supplements (including St. John’s Wort), vitamins up to 2 weeks or 5 half-lives of the

respective drug (whichever is longer) before the first administration of IMP and during the clinical part of the study, unless required to treat an AE. This does not include oral contraceptives not exceeding 30µg ethinyl estradiol or postmenopausal hormone replacement therapy or implants, patches, or IUDs/IUSs delivering progesterone (for female study participants).

15. Study participant tests positive for human immunodeficiency virus 1/2 antibodies (HIV-1/2-Ab), hepatitis B surface antigen (HBsAg), or hepatitis C virus antibody (HCV-Ab).
16. Study participant has > upper limit of normal (ULN) of any of the following: ALT, AST, ALP, or total bilirubin ( $\geq 1.5 \times \text{ULN}$  total bilirubin if known Gilbert's syndrome). If study participant has elevations only in total bilirubin that are >ULN and <1.5xULN, fractionate bilirubin to identify possible undiagnosed Gilbert's syndrome (ie, direct bilirubin <35%). To be enrolled, study participants must have ALT, AST, or ALP values within the ULN.
17. Tests that result in ALT, AST, or ALP up to 25% above the exclusion limit may be repeated once for confirmation. If out of range again, the study participant cannot be included.
18. Study participant has clinically relevant out-of-range values for hematology, and clinical chemistry, or urinalysis variables at the Screening Visit.
19. Study participant has any clinically significant abnormal physical examination and vital signs at the Screening Visit or confinement.
20. Study participant has any clinically relevant ECG finding at the Screening Visit or confinement. Study participant has an abnormality in the 12-lead ECG that, in the opinion of the investigator, increases the risks associated with participating in the study. In addition, any study participant with any of the following findings will be excluded: (a) QT interval corrected for heart rate using Bazett's formula (QTcB) or Fridericia's formula (QTcF) >450ms in 2 of 3 ECG recordings; (b) other conduction abnormalities (defined as PR interval  $\geq 220$ ms); (c) irregular rhythms other than sinus arrhythmia or occasional, rare supraventricular or rare ventricular ectopic beats. In case of an out of range result, 1 repeat will be allowed. If out of range again, the study participant cannot be included.
21. Study participant performs heavy physical exertion less than 3 days before confinement.
22. Study participant has a history within the last 5 years or present condition of malignancy, with the exception of basal cell carcinoma.
23. Study participant ingests grapefruit (as beverage, fruit, or supplements) within 72 hours before each administration of IMP. If this is the case at the start of the study, study participants may be rescreened.
24. Female study participant tests positive for pregnancy, plans to get pregnant during the participation in the study, or who is breastfeeding.

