The preclinical pharmacology studies indicated that the metabolism of PSL may be affected by extrinsic influences on the CYP3A4/CYP2C19 pathway. In order to mitigate any risk caused by these interactions, medication or dietary ingredients that induce, inhibit, or are a substrate for the CYP3A4/CYP2C19 pathways are restricted. Further details are provided in [Section 7.8.2](#) and [Section 7.8.3](#), respectively.

In clinical trials, PSL had a good safety profile. There were no deaths. Adverse events experienced by study participants receiving single and repeated doses of PSL were limited principally to CNS effects and that these were consistent with its known pharmacology. Adverse events were dose-related in frequency and intensity, self-limiting, and tended to decrease in intensity over the first few days of dosing. Some new AEs (mainly headache and sleep disturbance) developed after dose discontinuation with PSL in the Phase 1 studies, indicating a potential withdrawal syndrome. These have been mild, transient, not dose-related and not of clinical concern.

The occurrence of acute psychiatric serious adverse events (SAEs) (delirious syndrome, mania-like symptoms, and acute psychosis) in 3 study participants administered PSL highlights the need to maintain vigilance for such events. Reported acute psychiatric effects are consistent with adverse effects of other anticonvulsant drugs with various mechanisms of action. These SAEs were transient, acute, and required clinical intervention (admission to psychiatric care and antipsychotics). In healthy study participants, those SAEs occurred early after initiation of PSL done without titration; in 1 study participant, symptoms worsened upon abrupt drug discontinuation. Only in 1 out of 68 epileptic study participants exposed to PSL, a psychotic effect emerged a few weeks following dosing start after improvement in seizure control. This suggests a “forced normalization” phenomenon, which is described with other AEDs in resistant patients and is not unexpected with a potent AED (Loganathan et al, 2015; Clemens, 2005). The mitigation plan for acute psychiatric effects involves gradual titration and taper, known to improve tolerability of AEDs.

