#### **5.2.2.1 Treatment Period 1 and Treatment Period 2 (Day 1 to Day 11 and Day 12 to Day 22)**

Treatment Period 1 and Treatment Period 2 each consist of 5 days of treatment, followed by 1 week of wash-out.

During Treatment Period 1 and Treatment Period 2, study participants will receive PSL 100mg bid for 4 days (Day 1 to Day 4 and Day 12 to Day 15). On the fifth day (Day 5 and Day 16), 100mg of PSL will be given as a single dose in the morning. Study participants then enter 1 week of wash-out (from the evening of Day 5 to Day 11 and evening of Day 16 to Day 22).

Predose and postdose blood (venous and MITRA) and urine samples will be collected for PK analysis throughout the study (more details are provided in [Section 5.3](#)).

On Day 7 and Day 18, during the wash-out period, study participants will be discharged at the Investigator's discretion. Study participants may continue being confined to the unit at the Investigator's discretion. Study participants will check back into the unit on Day 10 and Day 21. Study participants will undergo the triplicate 12-lead ECG run-in on Day 11 and Day 22.

Study participants will be asked about the occurrence of AEs at check-in on Day 10, and via telephone contact on Day 20.

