### **5.3.1 Venous blood**

Venous blood samples for PK analysis will be performed as follows:

- Predose and 0.25h, 0.5h, 0.75h, 1h, 1.25h, 1.5h, 2h, 3h, 4h, 6h, 8h, and 12h post first dose of PSL during each Treatment Period (Day 1, Day 12, and Day 26)
- Predose and 0.25h, 0.5h, 0.75h, 1h, 1.25h, 1.5h, 2h, 3h, 4h, 6h, 8h, 12h, 24h, 36h, 48h, and 72h post last dose of PSL during Treatment Period 1 (Day 5) and Treatment Period 2 (Day 16)

- Predose and 0.25h, 0.5h, 0.75h, 1h, 1.25h, 1.5h, 2h, 3h, 4h, 6h, 8h, 12h, 24h, 36h, 48h, 60h, 72h, 96h, and 120h post last dose of PSL during Treatment Period 3b (on the morning of Day 33)

Additional PK trough samples will be taken immediately prior to each morning dose of PSL during Treatment Period 1 (Day 2 through Day 4) and Treatment Period 2 (Day 13 through Day 15) and each morning combination dose during Treatment Period 3b (Day 27 through Day 33).

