### **7.8.3 Diet, fluid, and activity control**

During each treatment period, study participants will complete a light meal 30min prior to each morning dose of IMP, and a standard meal 30min prior to each evening dose of IMP. On the

ECG run-in days where study participants do not receive IMP (that is, Day -1, Day 11, and Day 22, see [Section 10.3.3](#)), study participants will receive a light meal in the morning and a standard meal in the afternoon and evening at approximately the same time as it is expected to be given on the subsequent dosing days.

Study participants should keep their usual diet (besides the restrictions for the study) necessary for the maintenance of good health; excessive food consumption should be avoided. Study participants should refrain from heavy physical exertion (eg, vigorous exercise) from 3 days prior to (first) confinement and during the study.

Study participants should not consume more than 3 units alcohol/day (females) and 4 units alcohol/day (males), or more than 600mg of caffeine/day (200mL of coffee contains approximately 100mg of caffeine, 200mL of black tea approximately 30mg, and 200mL of cola approximately 20mg) from 48 hours prior to each administration of PSL and until the final PK plasma sampling of each dosing period.

Grapefruit (as beverage, fruit, or supplements) within 72 hours before each administration of IMP will not be allowed. If this is the case at start of study, study participants may be rescreened.

Study participants must refrain from donating blood or plasma during the course of the study (except for the samples taken for the purpose of the study) and should refrain from donating blood or plasma for at least 3 months prior to the Screening Visit and until 2 months after the end of the study.

Water will be available ad libitum except for between 1 hour before and 2 hours after dosing. A total of 240mL of water will be given to each study participant at the time of administration of IMP.

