### **8.3.5 Day 10 (Treatment Period 1) and Day 21 (Treatment Period 2)**

Study participants will check into the unit of Day 10 and Day 21, 2 days prior to receiving the first dose in Treatment Period 2 (on Day 12) and Treatment Period 3 (Day 23). The following procedures/assessments will be performed on Day 10 and Day 21:

- C-SSRS
- Full physical examination
- Prior and concomitant medications
- Vital signs (including systolic and diastolic BP, pulse rate, respiration rate, and oral temperature)
- Blood and urine samples for the following clinical laboratory tests will be collected:
  - Serum pregnancy test (for women of childbearing potential only)
  - Hematology, serum chemistry, and urinalysis

- Urine and cotinine drug screen
- Alcohol breath test
- Triplicate 12-lead ECGs
- Recording of AEs/medical procedures

Study participants will undergo the triplicate 12-lead ECG run-in on Day 11 and Day 22 (see [Section 8.3](#)).

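### The grapefruit ban in Protocol Section 7.8.3 has no post-dose part, so it lapses during PSL-alone sampling; the practical exposure is the 72 h sample behind the secondary λz and t1/2,ss

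*Protocol*

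**What the plan says.** The operative rule is in Protocol Section 7.8.3: "Grapefruit (as beverage, fruit, or supplements) within 72 hours before each administration of IMP will not be allowed". Exclusion criterion 23 (Section 6.2) uses the same window: "Study participant ingests grapefruit (as beverage, fruit, or supplements) within 72 hours before each administration of IMP". Both look backwards from a dose, and neither says what applies after one.

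The alcohol and caffeine limits in Section 7.8.3 are framed differently. They apply "from 48 hours prior to each administration of PSL and until the final PK plasma sampling of each dosing period".

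Section 2.3 gives the reason for dietary control: "medication or dietary ingredients that induce, inhibit, or are a substrate for the CYP3A4/CYP2C19 pathways are restricted". It refers to Section 7.8.3 for the dietary details, and grapefruit is the only specific food barred there.

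On timing, Section 5.2.2.1 states: "On the fifth day (Day 5 and Day 16), 100mg of PSL will be given as a single dose in the morning". The next IMP is PSL on Day 12 and erythromycin on Day 23 (Section 8.3.5). Venous and MITRA sampling after the Day 5 and Day 16 doses runs from 0.25 h to 72 h (Sections 5.3.1 and 5.3.2).

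On confinement, Section 5.2.2.1 states: "On Day 7 and Day 18, during the wash-out period, study participants will be discharged at the Investigator's discretion". Participants then come back on Day 8 or Day 19 for the 72 h sample (Section 8.3.3).

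**The concern.** This study measures the effect of CYP3A4 inhibition on PSL. The food that the protocol restricts on enzyme grounds has a shorter window than alcohol and caffeine, and that window closes when the last PSL-alone dose is swallowed. As written, fruit or juice is allowed while the PSL-alone elimination phase is still being sampled.

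No other passage closes the gap. Section 5.2.2 asks the investigator to explain prohibited foods for the wash-out but refers to Section 7.8.2, which lists medicines and supplements and no foods. The Day 8 and Day 19 visits and the Day 9 and Day 20 telephone contacts ask about adverse events and concomitant medication or treatment, not diet. Intake could go unrecorded.

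At stake are λz and t1/2,ss for PSL alone. If grapefruit slows PSL elimination, which is the apparent reason for restricting it, intake before the 72 h sample would lengthen the PSL-alone half-life and narrow its descriptive contrast with Period 3b.

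**Working it through.** The plan gives no figure to reproduce. The check compares the ban with the sampling calendar. Morning doses are taken as 0 h of the day and evening doses as +12 h (an assumption). Erythromycin counts as an IMP, as Protocol Section 7.1 lists it.

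**When the ban is off**

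| Last PSL-alone dose | Next IMP | Interval | Ban resumes (interval − 72 h) |
|---|---|---|---|
| Day 5, morning | Day 12 | 7 × 24 = 168 h | 168 − 72 = 96 h, i.e. Day 9 |
| Day 16, morning | Day 23 | 7 × 24 = 168 h | 168 − 72 = 96 h, i.e. Day 20 |

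**Samples in that gap.** Section 5.3.1 lists 12 post-dose samples from 0.25 h to 12 h, then 24, 36, 48 and 72 h: 12 + 4 = 16 per period. The last, at 72 h, precedes 96 h. On the wording alone, the ban covers 0 of 16. The 12 h profiles on Days 1, 12 and 26 are covered, because twice-daily dosing continues after them.

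**Samples taken in the unit.** Participants stay in the unit on Day 6 and Day 17 (Section 8.3.1) and are discharged on Day 7 or Day 18 after the 48 h procedures (Section 8.3.2). Discharge is thus at about (7 − 5) × 24 = 48 h.

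- Confined: 15 of 16 samples, including the whole 0–12 h AUCτ interval, which ends 48 − 12 = 36 h before discharge.
- After discharge: 1 of 16, the 72 h sample. It is one of the four samples from 24 h on.
- Urine collection in Periods 1 and 2 ends at 48 h (Section 5.3.3), so it closes at discharge.

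**Period 3b.** The last erythromycin dose is (37 − 33) × 24 + 12 = 108 h after the Day 33 PSL dose. The ban covers 18 of 19 post-dose samples; the 120 h sample is 12 h outside it. Participants are in the unit until Day 38 in any case.

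**Parameters that use the 72 h sample.** Of the plasma PSL parameters in Section 4.1, only λz and t1/2,ss draw on it. The listed metabolite parameters are Cmax and 12 h AUC measures and their ratios to parent. CL/Fss is taken here as dose over AUCτ; this is an assumption, since the SAP gives no formula and its flagging rule in Section 2.2.1.2 names CL/Fss as half-life-derived.

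**What the analysis does with them.** SAP Sections 9.1 and 9.2 plan ratios with 90% CIs for Cmax, AUC(0-12), Cmax,ss and AUCτ only. λz and t1/2,ss are summarised descriptively.

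**The case against.** The strongest case on the other side is that little of consequence remains once confinement is counted. Most of it stands.

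- **Primary variables.** A reader might infer that AUCτ and Cmax,ss on Day 5 and Day 16 are left open to contamination. The documents do not support that. Both come from the first 12 h after dosing, in the unit, with meals set around dosing. No passage says that unit menus exclude grapefruit, but none shows a realistic route to intake.
- **Bias in the interaction estimate.** A reader might infer that a ban lifted for the PSL-alone profiles and kept for Period 3b pulls the erythromycin ratio down. The planned ratios do not use half-life, and confinement protects the Period 3b profile whatever the ban says. The difference in wording also depends on erythromycin counting as an IMP. If the rule were read as PSL only (SAP Section 3.2.1 takes PSL as the IMP reference for relative day), all three terminal profiles would lie outside it.
- **Supplements.** A reader might infer that no grapefruit intake in the gap would be a deviation. Section 7.8.2 and exclusion criterion 14 already bar dietary supplements during the clinical part of the study. The gap concerns fruit and beverage.
- **The 72 h sample may not matter.** Post-Cmax values below quantification are treated as missing (SAP Section 4.2.1), and the 24, 36 and 48 h samples meet the SAP's three-point minimum for half-life. This stands only in part. Those three samples span 48 − 24 = 24 h, so on their own they meet the SAP's two-half-life condition only if t1/2 is 12 h or less, and the documents give no PSL half-life.

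The difference between the two windows in Section 7.8.3, and the misdirected cross-reference in Section 5.2.2, survive all of this.

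**Conclusion.** The gap in the wording is real, and its practical reach is small. The ban is off for 96 h after each last PSL-alone dose while sampling continues to 72 h. Realistic exposure is fruit or juice between discharge (about 48 h) and 72 h, ahead of one sample in each of Periods 1 and 2. Among the derived parameters, only the secondary λz and t1/2,ss can be affected. The primary comparison is not in question.

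The documents give no figure for the effect of grapefruit on PSL, so the size cannot be calculated; it is likely small, and nil where the 72 h value is below quantification. The direction, a longer PSL-alone half-life, assumes that grapefruit acts as the CYP3A4/CYP2C19 rationale in Section 2.3 implies. The exposure also assumes discharge on Day 7 and Day 18; participants kept in the unit longer have less of it or none.

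This is a cheap improvement and does not threaten the study's conclusions.

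**What to change.** 1. In Protocol Section 7.8.3, bring the grapefruit window into line with the alcohol and caffeine window. For example: *Grapefruit fruit, beverage and supplements are not permitted from 72 hours before the first IMP administration until the final PK sample (Day 38).* This closes the gap whether or not erythromycin is read as an IMP. A lighter alternative keeps the 72 h lead-in and extends the ban through the final PK sample of each dosing period.
2. In Section 5.2.2, direct the wash-out instruction on foods to Section 7.8.3, keeping Section 7.8.2 for medications.
3. Optionally, limit exclusion criterion 23 to the 72 h before the first administration, since an entry criterion cannot be applied to later doses. Closing the gap does not depend on this.

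The cost is one sentence, one cross-reference and the matching participant instructions, with no new procedure. The example wording adds about 2 × 96 h = 192 h, or 8 grapefruit-free days per participant, plus about 12 h before the Day 38 sample while participants are still in the unit. The lighter alternative adds 2 × 72 h = 144 h, or 6 days, plus the same 12 h.

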### 6.3 Withdrawal criteria

Study participants are free to withdraw from the study at any time, without prejudice to their continued care.

Study participants must be withdrawn from the study if any of the following events occur:

1. Study participant develops a clinically relevant medical condition (or laboratory parameter) that, in the opinion of the Investigator, jeopardizes or compromises the study participant's ability to participate in this study or makes it unsafe to continue (for example a psychiatric event).
2. Study participant withdraws his/her consent.
3. The Sponsor or a regulatory agency requests withdrawal of the study participant.
4. An ECG shows an absolute QTcF value  $>500\text{ms}$  or  $>60\text{ms}$  prolongation above Baseline (defined as the mean of triplicate ECG taken at predose on Day 1, Day 12, Day 23 or Day 26) in 1 or more ECG recordings.
5. Study participant develops second- or third-degree atrioventricular block or another clinically relevant change in ECG results as determined by the Investigator.
6. Refer to [Section 6.4.1](#) for withdrawal criteria in relation to potential drug-induced liver injury (PDILI).
7. Study participant tests positive for pregnancy at any point during the study.

Study participants may be withdrawn from the study if any of the following events occur:

8. Study participant is noncompliant with the study procedures or IMP in the opinion of the Investigator.
9. Study participant takes prohibited concomitant medications as defined in this protocol.

If the withdrawal occurs following dosing with IMP, the study participant will be asked to return for the EOS Visit 7 to 10 days after last intake of IMP.

The Investigator should attempt to obtain information on study participants in the case of withdrawal or discontinuation. For study participants considered as lost to follow up, the Investigator should make an effort (at least 1 phone call and 1 written message to the study participant), and document his/her effort (date and summary of the phone call and copy of the written message in the source documents), to complete the final evaluation. All results of these evaluations and observations, together with a narrative description of the reason(s) for removing the study participant, must be recorded in the source documents. The electronic Case Report form (eCRF) must document the primary reason for withdrawal or discontinuation.

Investigators should contact the Sponsor Study Physician, whenever possible, to discuss the withdrawal of a study participant in advance.

